This study will evaluate the changes in respiratory mechanics following TBI and determine the effect of inhaled nitric oxide on gas exchange.

4. Purpose of Study:

[figure not shown]
To determine the changes in respiratory mechanics in patients with traumatic brain injury (within 36 hours of admission and day 3 following admission).

To evaluate the effect of inhaled nitric oxide on gas exchange in patients with traumatic brain injury within 36 hours of admission.

Hypothesis: Inhaled nitric oxide improves oxygenation and reduces deadspace to tidal volume ratio following TBI.

5. Background:

Intubation and mechanical ventilation are common treatments in the care of patients with traumatic brain injury (TBI). Intubation allows for airway control and facilitates removal of respiratory secretions. Mechanical ventilation allows control of arterial carbon dioxide to aid in control of intracranial pressure. Recent evidence suggests that lung protective ventilation (tidal volumes of 6 ml/kg of predicted body weight and moderate positive end expiratory pressure) improves outcomes following brain injury and reduces brain-lung cross talk. Figure 1.

Respiratory failure following traumatic brain injury is a common complication resulting in hypoxemia and is associated with release of inflammatory mediators which may damage distal organs including the brain. The etiology of respiratory

failure following brain injury is multifactorial. Isolated head trauma is associated with neurogenic pulmonary edema and changes in ventilation perfusion matching. Concomitant trauma to the chest and pulmonary contusion may further worsen lung injury. It has been suggested that brain injury primes the lung to be a greater risk to a second hit (pneumonia, ventilator induced lung injury, lung contusion). Loss of consciousness can lead to aspiration of oral or gastric contents leading to pneumonia. Importantly, respiratory failure following TBI is implicated in 50% of deaths and prolonged ICU and hospital stay. (4,5)

The treatment of respiratory failure in TBI must balance the need to improve lung function with the negative consequences of increased intrathoracic pressure on mean arterial pressure, intracranial pressure and venous return. Traditional treatment of increasing PEEP and mean airway pressure then, represent competing interests. Methods for improving arterial oxygenation while avoiding negative hemodynamic effects are needed.

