Mechanical ventilation following TBI is provided with the normal goals, reduce the work of breathing, provide adequate oxygenation, maintain normo- or hypocapnia and avoid lung injury. However, in an effort to improve brain tissue PaO_2 (TbO_2) mechanical ventilation in TBI may include increases in mean airway pressure and FIO_2 unrelated to the degree of lung dysfunction. Ventilatory support is always a balance of competing interests. Increases in airway pressure by increasing tidal volume, prolonging inspiratory time or increasing PEEP must be balanced against the risk of lung injury and hemodynamic interference. In TBI these must be furthered balanced against the impact on mean arterial pressure, cerebral perfusion pressure and venous return. (6)

Inhaled nitric oxide (INO) is a selective pulmonary vasodilator that at low doses (5-20 ppm) improves V/Q matching and at higher doses (80 ppm) reduces pulmonary artery pressures. Nitric oxide plays a role in a number of biologic processes and pathways that have been associated with improvements in brain function. (7,8) INO has been used in patients with TBI with successful increases in oxygenation in small case series. (10-11). These reports are not systematic applications of INO but rather rescue therapy in the face of ARDS.

The use of INO in ARDS has not proven to impact outcomes. (12-13) Several studies have shown improved gas exchange but no changes in morbidity or mortality. Despite these findings, INO is often used in ARDS to help improve gas exchange without increasing the risk of lung injury by increasing lung volumes or pressures.

This study will determine the etiology of lung dysfunction following TBI and describe the effect of INO on cardiorespiratory variables.

Inhaled nitric oxide (INOmax) is FDA approved and delivered via the INOmax DS_{IR} and FDA cleared delivery and monitoring device. The use of inhaled nitric oxide is limited to a maximum of 80 ppm. We will deliver 20 ppm, a dose that is widely prescribed.

6. Study design:

This study will determine the impact of inhaled nitric oxide on gas exchange and hemodynamics in a series of up to 43 patients with TBI over an 18 month period. The delivery of INO will be blinded. The study will also describe the changes in respiratory mechanics over a 3 day period.

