5. Positive end expiratory pressure (PEEP) will be titrated from baseline PEEP as set at time of enrollment to 15 cm H_2O (in 5-cm H_2O increments) while measuring all the variables listed in #1-4 above. This method will determine the best PEEP and determine recruitability of the lung. FRC will be measured at three levels of PEEP from baseline to a maximum of 15 cm H_2O . This is an automated measurement requiring approximately 15 minutes to complete. If the patient develops hypotension (systolic pressure < 90 mm Hg or mean arterial pressure < 60 mm Hg) participation in the PEEP trial will be terminated.
6. Following these initial measurements, patients will be randomized to receive either a placebo (nitrogen and oxygen) or inhaled NO at 20 ppm for 2 hours \pm 30 minutes. After receiving the placebo or inhaled NO, the measurements in #1-4 will be reassessed (no change in PEEP will be made during this time unless required for clinical purposes).
7. If the patient remains on the ventilator at day 3 (72 hours after admission), 1-6 above will be repeated.

Subjects will receive placebo or drug for no more than 5 hours total.

If the patient responds to NO with a brisk increase in SpO₂ or PaO₂ – sudden withdrawal of NO can result in a fall in oxygenation (rebound pulmonary hypertension). This is uncommon in the absence of pulmonary hypertension. Prevention of rebound pulmonary hypertension is accomplished by increasing FIO₂ by 10-20% prior to discontinuation of NO, followed by a return to baseline FIO₂ over 30 mins.

If ICP goes up by >20% NO will be discontinued.

7. Research data collection/study procedures:

The patient baseline demographics including injury mechanism, severity and distribution, Glasgow coma scale score, age, gender, any witnessed aspiration, and lung mechanics measurements listed above will be collected to data sheets and then entered into a RedCap database. We will also record ventilator settings, lung compliance, airways resistance, dead space to tidal volume ratio, functional residual capacity, blood gases and duration of total mechanical ventilation, days in the ICU, hospital days and survival will be collected from the medical record and also entered into the RedCap database. See sequence of events for study measures.

8. Specimen collection:

The following blood samples will be taken:

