At baseline up to 3.5 ml will be taken. 1.5 ml for arterial blood gas testing (tests include: arterial pH, PaCO₂, PaO₂, SaO₂ and HCO₃) and 2 ml for measurement of inflammatory mediators specific to the lung.

After 90 to 120 minutes of nitric oxide/placebo delivery, less than 1.5 ml will be taken for arterial blood gas testing.

At the end of the study, up to 3.5 ml will be taken. 1.5 ml for arterial blood gas and 2 ml for measurement of inflammatory mediators specific to the lung.

The blood will be taken from indwelling lines when possible. If we are unable to obtain any of the blood samples, the subject will remain in the study and all other data will continue to be collected

9. Potential Benefits:

The detailed measurement of respiratory mechanics will be provided to the clinical team. This information which is not routinely measured can be used to optimize ventilator support beyond traditional monitoring. The determination of FRC and recruitability of the lung may assist the clinical team in identifying the best PEEP for each individual patient.

If the patient has a significant increase in PaO_2 associated with INO/placebo delivery, the clinical team can use that information to implement INO therapy as part of clinical care. It is unlikely that placebo will increase oxygenation appreciably. We will not unblind the study, the clinical team will have to make this decision based on a supposition of INO delivery.

Understanding the changes in respiratory function following TBI and the response to INO may improve treatment regimens for future patients.

10. Potential Risks, Discomforts, and inconveniences:

Level of risk: Greater than minimal risk.

The measurements to be made utilize non-invasive measures of lung volumes, flows, and pressures to determine mechanics.

Arterial puncture/venipuncture may cause pain/discomfort, bruising, fainting, and infection from phlebotomy sites.

Hypotension in severe pulmonary hypertension and left ventricular failure (very uncommon).

Methemoglobinemia has only been reported at 80ppm.

The stepwise increase in PEEP to determine changes in FRC will be limited to a maximum of 15 cm H_2O . PEEP can decrease venous return and cause transient hypotension. The risk of hemodynamic compromise at these low pressures is small. All subjects will have blood pressure and heart rate continuously monitored (as is standard of care) throughout the measurements.

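### The research PEEP titration to 15 cm H2O has a hypotension stop but no ICP stop, and the day-3 repeat has no ICP re-check

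*Combined protocol and SAP*

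**What the plan says.** All places are in the combined protocol and SAP.

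- **Section 5 (Background; the first point is also in section 3).** Treatment of respiratory failure in brain injury is weighed against the "negative consequences of increased intrathoracic pressure on mean arterial pressure, intracranial pressure and venous return". The text continues: "Traditional treatment of increasing PEEP and mean airway pressure then, represent competing interests". Later, after a sentence that lists raising PEEP among the ways to increase airway pressure: "In TBI these must be furthered balanced against the impact on mean arterial pressure, cerebral perfusion pressure and venous return".
- **Section 6, item 5.** PEEP goes from its level at enrolment up to 15 cm H2O in 5-cm steps, with mechanics, dead space and FRC measured along the way. The only stop is hypotension: "systolic pressure < 90 mm Hg or mean arterial pressure < 60 mm Hg) participation in the PEEP trial will be terminated".
- **Section 6, item 6.** Study gas comes next: "Following these initial measurements, patients will be randomized to receive either a placebo" or nitric oxide at 20 ppm. PEEP is then left alone unless clinical care needs a change.
- **Section 6, item 7.** "If the patient remains on the ventilator at day 3 (72 hours after admission), 1-6 above will be repeated".
- **Section 6, after item 7.** "If ICP goes up by >20% NO will be discontinued".
- **Section 10.** On PEEP: "PEEP can decrease venous return and cause transient hypotension". Blood pressure and heart rate are listed as monitored during the measurements. ICP appears neither as a PEEP risk nor as a monitored variable.
- **Section 14.** Exclusions 6 and 13 keep out patients whose ICP is above 20 mmHg and needs bolus hypertonic saline, or stays above 20 mmHg for over 30 minutes despite treatment.

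**The concern.** The protocol identifies a hazard, carries out the manoeuvre linked to that hazard for research, and attaches its ICP stop to a different intervention. The authors evidently thought a numeric ICP stop was needed, since they wrote one for the gas. They also thought the PEEP steps needed a numeric stop, since they wrote one for blood pressure. The combination that their background calls for, an ICP stop for the PEEP steps, is absent.

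At stake is patient safety, not the validity of the primary comparison. If a monitored patient's ICP rises during the steps while blood pressure holds, ending the steps is left to whoever is at the bedside. At day 3 a patient who has developed uncontrolled ICP since enrolment still meets the only stated condition for a second titration, which is being on the ventilator.

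**Working it through.** The plan gives no figure on this point, so there is none to reproduce. The check is mostly a reading of the text, followed by a count of exposure.

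**1. Which rule applies at which step**

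| Step | Blood-pressure stop | ICP rule |
|---|---|---|
| Enrolment | Exclusions 5, 8, 15 | Exclusions 6, 13 |
| PEEP steps, first session (item 5) | Systolic < 90 or mean < 60 mm Hg | None stated |
| Gas, first session (item 6) | None stated | Stop NO if ICP rises > 20% |
| PEEP steps, day 3 (item 7) | As item 5 | None stated; exclusions not re-applied |
| Gas, day 3 (item 7) | None stated | Stop NO if ICP rises > 20% |

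**2. Could the gas rule be acting while PEEP is raised?** No. Item 6 starts gas after the initial measurements, and item 7 repeats items 1-6 in the same order. Gas lasts 2 hours ± 30 minutes per session, so at most 2 × 2.5 = 5 hours over two sessions, which matches the 5-hour cap in section 6. Gas from the first session is therefore over before the day-3 steps. During either titration the ICP rule has nothing to stop.

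**3. Number of titrations.** Up to 43 patients may be enrolled to obtain 38 evaluable (section 12).
- Ceiling: 43 × 2 = 86.
- If only the 38 evaluable patients reach day 3: 43 + 38 = 81.
- Number in ICP-monitored patients: the documents give no share. Assuming 25%, 50% or 100% of the ceiling: 0.25 × 86 = 21.5, 0.50 × 86 = 43, 1.00 × 86 = 86.

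**4. Time and size of the PEEP rise (assumptions stated).**
- Suppose two of three equal-length levels lie above baseline. With the 15 minutes in item 5 taken as the total, time above baseline is 15 × 2/3 = 10 minutes per session. With the 30 minutes in section 10, it is 30 × 2/3 = 20 minutes. If item 5's 15 minutes is per level, two levels take 2 × 15 = 30 minutes, but three levels would then take 45, more than section 10 allows for all measurements.
- With baseline PEEP of 5 (assumed), the rise is 15 − 5 = 10 cm H2O. With baseline 10, it is 15 − 10 = 5.

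**5. Would a bare > 20% trigger work?** At a reference ICP of 5, 10 or 15 mmHg it fires on a rise of more than 0.20 × 5 = 1, 0.20 × 10 = 2 or 0.20 × 15 = 3 mmHg. At low ICP that is very sensitive, so the rise should have to be sustained. The protocol's own limit of 20 mmHg is reached before a 20% rise once the reference exceeds 20 / 1.2 = 16.7 mmHg.

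**The case against.** The best case for leaving the plan alone is that the risk is already contained. Exclusions 6 and 13, with those for brain death, hemodynamic instability and pupil dilation, remove high-risk patients shortly before the first titration. PEEP is capped at 15 cm H2O and the time above baseline is short. Patients are in intensive care, research staff stay at the bedside (section 10), and the admitting physician and ICU attending must agree to enrolment (section 15). Section 7 also refers to a sequence of events that is not in the text available, so absence of a rule is certain only for the visible text.

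Much of this stands, and it limits how serious the point is. It does not supply the missing rule. The exclusions are entry criteria, and their protection is weakest at day 3. The medical monitor's stated power is to halt enrolment (section 11), not to end a titration. The sequence of events is described as covering study measures.

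Three stronger readings are tempting but unsupported:
- **That the titration is shown to be harmful.** The documents give no size for the effect of PEEP on ICP and no share of patients monitored.
- **That it permits a dangerous cerebral perfusion pressure.** One could subtract an assumed ICP from the mean pressure limit of 60 mm Hg, but a low result would reflect the low blood pressure, not an effect of PEEP. The protocol sets no perfusion-pressure limit.
- **That staff must continue through an ICP rise.** Nothing in the text bars clinicians from lowering PEEP.

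**Conclusion.** The point holds as a patient-safety gap that should be fixed. In the visible text, no written ICP criterion ends the PEEP steps at either session, and the ICP exclusions are not re-applied before the day-3 steps, although the protocol names ICP as a harm of raised intrathoracic pressure in these patients.

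Its size can be stated only as exposure. The range of 81 to 86 titrations assumes that every enrolled patient has the first titration and that 38 to 43 patients reach day 3; earlier dropout would lower it. The part that an ICP rule could reach depends on the unknown monitored share. With harm unquantified and exposure brief, capped and attended, the evidence does not support a more severe rating. The primary endpoint, its test and the 19 per group are not in question.

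**What to change.** Amend the protocol as follows, for patients already monitored for ICP:

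1. **Item 5.** End the PEEP trial and return PEEP to baseline if ICP shows a sustained rise of more than 20% above the reading taken just before that session's first PEEP step, or exceeds 20 mmHg. The medical monitor sets the duration that counts as sustained.
2. **Item 7.** Before the day-3 PEEP steps, re-check exclusions 6 and 13. If either is met, skip only the PEEP steps and still take the blood gas that the primary endpoint needs.
3. **Section 10.** Add ICP rise to the PEEP risks, and ICP to the monitored variables where a monitor is in place.

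The cost is about one paragraph of amendment and no new equipment. Gas delivery and sample size do not change. The real downside is lost data: some mechanics and FRC values at the upper PEEP levels will be missing, and selectively so, because the patients stopped are those whose ICP responds to PEEP or is already high. Describing respiratory mechanics is a stated purpose of the study (section 4), though section 12 plans only descriptive summaries of it. The report should therefore give the number of titrations stopped early or skipped, with reasons.

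### The plan's hypotension limits end only the PEEP trial; no blood pressure limit is written for starting, continuing or repeating study gas

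*Combined protocol and SAP*

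**What the plan says.** All of the rules on study gas in the supplied text are in section 6.

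- **Item 5 (PEEP titration).** The hypotension rule is: "systolic pressure < 90 mm Hg or mean arterial pressure < 60 mm Hg) participation in the PEEP trial will be terminated". That is its whole stated consequence.
- **Item 6 (gas).** "Following these initial measurements, patients will be randomized to receive either a placebo" or inhaled NO at 20 ppm, for 2 hours give or take 30 minutes. No pressure condition is attached.
- **Item 7 (repeat).** "If the patient remains on the ventilator at day 3 (72 hours after admission), 1-6 above will be repeated". No re-check of the section 14 exclusions is written.
- **After item 7.** Total gas time is capped at 5 hours, an FIO2 step is described for withdrawing NO, and the one physiological trigger is stated: "If ICP goes up by >20% NO will be discontinued".

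Section 10 lists this risk: "Hypotension in severe pulmonary hypertension and left ventricular failure (very uncommon"). It also says: "All subjects will have blood pressure and heart rate continuously monitored (as is standard of care) throughout the measurements". Neither sentence is tied to an action on the gas. Section 11 lets the medical monitor halt enrollment and does not mention stopping gas in an individual patient.

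Section 14 excludes, at entry, systolic pressure below 100 mm Hg or arrhythmia (exclusion 5), spinal cord injury with hypotension (8), known heart failure defined as EF below 20% (14), and CVP above 20 mm Hg with systolic below 100 mm Hg (15).

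**The concern.** The plan treats a systolic pressure of 85 mm Hg during PEEP titration as a reason to stop. It gives no instruction if the same reading appears during the gas session that follows. Section 5 itself says that ventilatory support after brain injury has to be weighed against mean arterial and cerebral perfusion pressure. An ICP trigger does not see a fall in mean arterial pressure, which lowers perfusion pressure even when ICP is unchanged.

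At stake is the safety of individual patients and the clarity of the bedside instruction. Blinded ICU staff have no written pressure limit for a gas whose identity they do not know. The sample size and the test are not in question.

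**Working it through.** The plan has no figure for this point, so the check is mainly a reading of each rule against each stage.

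| Stage | Written pressure condition | Consequence |
|---|---|---|
| Entry (section 14) | Systolic < 100 mm Hg, and exclusions 8 and 15 | Not enrolled |
| PEEP trial (item 5) | Systolic < 90 or mean arterial < 60 mm Hg | PEEP trial ends |
| Start of gas, first session (item 6) | None | None |
| During gas (item 6) | None; ICP rise > 20% only | NO discontinued |
| Day 3 repeat (item 7) | Item 5 limits again, for the PEEP step only | PEEP trial ends |
| Day 3 gas (items 6 and 7) | None; ICP rise > 20% only | NO discontinued |

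Three things follow.

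1. **A failed PEEP trial does not hold back the gas.** Item 6 comes after item 5 and does not say what happens to a patient whose PEEP trial was ended for hypotension.
2. **The entry screen is old by day 3.** Section 15 allows enrollment up to 36 hours after admission and item 7 acts at 72 hours. The gap is therefore at least 72 − 36 = 36 hours, with no written re-check.
3. **The entry screen leaves some risk.** A patient may enter at systolic 100 mm Hg, which is 100 − 90 = 10 mm Hg above the item 5 limit. Pulmonary hypertension is not an exclusion, and an EF of 20% or more is not excluded by exclusion 14.

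**Exposure that the wording covers.** One session is 120 ± 30 minutes, so 90 to 150 minutes. Two sessions at the upper end give 2 × 150 = 300 minutes = 5 hours, which reproduces the stated cap. With up to 43 patients:

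- one 90-minute session each: 43 × 1.5 h = 64.5 patient-hours;
- two 150-minute sessions each: 43 × 5 h = 215 patient-hours.

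With equal allocation (section 12 plans 19 per group), half of this is NO: 32.25 to 107.5 patient-hours. These figures measure exposure, not risk. The documents give no rate of hypotension during gas.

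**Allowance.** Section 12 enrolls up to 43 to obtain 38 evaluable patients, so 43 − 38 = 5 may be lost. Section 8 plans the on-gas blood gas at 90 to 120 minutes. A stop before 90 minutes can therefore lose that sample.

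**The case against.** The case against giving this weight is a fair one, and several parts of it stand.

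- **The named hazard is narrow.** A reader might infer that NO is expected to lower pressure across the whole sample. The documents do not support that. Section 10 confines the risk to severe pulmonary hypertension and left ventricular failure and calls it very uncommon. Section 5 describes NO as acting selectively on the pulmonary vessels, at a commonly used dose. Exclusions 5, 8, 14 and 15 reduce the risk further, though pulmonary hypertension and an EF of 20% or more remain eligible.
- **PEEP and gas differ.** The item 5 limits suit PEEP, which reduces venous return. NO does not share that mechanism, and the placebo has no stated hypotensive effect. A brief fall at high PEEP need not bar gas once pressure has recovered. This stands, and is why the fix withholds gas only while pressure is below the limit.
- **Staff will act anyway.** Patients are in an ICU with continuous pressure monitoring, and nothing stops clinicians from turning the gas off. A reader might infer that patients are left unattended during gas. The text does not say so: section 10 places research staff at the bedside for the measurements, about 30 minutes, and is silent on the gas period.
- **The rule may exist elsewhere.** Section 7 ends with "See sequence of events for study measures". That item and the consent pages are not in the supplied text.

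None of this supplies a written pressure limit for the gas. It lowers the priority of the point without removing it.

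**Conclusion.** The concern holds as a gap in the supplied text. The item 5 limits apply to the PEEP trial alone, an ICP rise of more than 20% is the only physiological stop for gas, and gas is started and repeated without a pressure condition or a re-check of the entry limit. Following the plan as written permits blinded gas to be started or continued in a hypotensive brain-injured patient.

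The wording reaches every patient, up to 43 and at most 215 patient-hours of gas, but the hazard that the plan itself names concerns a small and partly excluded subgroup. The number who would meet the limit cannot be derived from the documents, and any assumed rate would describe hypotension from all causes, not harm from the gas or harm avoided by stopping it. A reader might go on to infer demonstrated harm or a weakened trial; the documents support neither.

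This is a low-priority, cheap safety improvement with no claimed effect on power or inference. It rests on the assumption that the unsupplied sequence of events and consent pages contain no such rule.

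**What to change.** Replace the ICP sentence in section 6 with:

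*Blinded study gas will be discontinued, using the FIO2 step above, if ICP (where monitored) rises by >20%, or if systolic pressure is < 90 mm Hg or mean arterial pressure is < 60 mm Hg on a confirmed reading. Gas will not be started at either session while pressure is below these limits. Patients stopped early stay in their randomized group, and the time and reason are recorded.*

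The limits are the sponsor's own. A confirmed reading guards against stops for artefact. Referring to blinded study gas, rather than NO, lets staff act without knowing the arm. The words on monitoring are needed because no criterion requires an ICP monitor. If the sequence of events already holds such a rule, a cross-reference is enough.

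**Cost.** Three sentences and one database field. Pressure is already monitored, so there is no new equipment and no change to eligibility. The downside is a few early stops in either arm. A stop before 90 minutes can lose that session's on-gas blood gas. Section 8 says "If we are unable to obtain any of the blood samples, the subject will remain in the study", but that does not make the subject evaluable. Section 12 does not say which Day 3 sample defines the primary endpoint. If it is the on-gas sample, an early stop on Day 3 can leave the endpoint missing and use part of the 5-patient allowance.

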Research personnel will remain at the bedside throughout the measurements of respiratory mechanics which will require approximately 30 minutes to complete.

11. Data Safety monitoring plan and/or DSMB:

[name] will act as medical monitor for the study. He will review subjects' research data and adverse events to ensure patient safety. The medical

monitor will have the power to temporarily or permanently halt enrollment if it is deemed that patient safety is compromised.

12. Data Analysis:

Descriptive statistics will be employed to summarize relevant patient demographic factors as well as on baseline measurement of clinical variables. As a check on the success of randomization, these variables will be compared between groups using t-tests or chi-square tests, as appropriate.

The primary endpoint for this study is a change in $\text{PaO}_2:\text{FiO}_2$ ratio of 20 percent or greater between baseline and Day 3. The proportions of patients achieving success according to this criterion will be compared between groups using a two-sided z-test with pooled variance.

Group sample sizes of 19 in group one and 19 in group two achieve 82% power to detect a difference between the group proportions of 0.40. The proportion in group one (the treatment group) is assumed to be 0.10 under the null hypothesis and 0.50 under the alternative hypothesis. The proportion in group two (the control group) is 0.10. The test statistic used is the two-sided Z test with pooled variance. The significance level of the test was targeted at 0.05. The significance level actually achieved by this design is 0.0361.

Respiratory mechanics will be presented as descriptive (Mean, SD, range). Up to 43 subjects may be enrolled, in order to obtain the required 38 evaluable subjects. Patients will be removed from the study and its analysis if extubated by the clinical treatment team during the 72 hour NO protocol.

13. Data storage and confidentiality (include sample storage if applicable)

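### Does the 20% change rule for PaO2:FiO2 count a deterioration as a success?

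*Combined protocol and SAP*

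**What the plan says.** Section 12 (Data Analysis) defines the primary outcome: "The primary endpoint for this study is a change in" PaO2:FiO2 "ratio of 20 percent or greater between baseline and Day 3". It continues: "The proportions of patients achieving success according to this criterion will be compared between groups using a two-sided z-test with pooled variance". Neither sentence says whether the change must be upward, and no other section gives an operational rule.

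Four other statements bear on direction:

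- Section 4 (Purpose of Study) gives the hypothesis: "Inhaled nitric oxide improves oxygenation and reduces deadspace to tidal volume ratio following TBI".
- Section 12 uses the word success for meeting the criterion.
- Section 12 says the treatment-group proportion "is assumed to be 0.10 under the null hypothesis and 0.50 under the alternative hypothesis", against 0.10 in controls.
- Section 9 (Potential Benefits) remarks: "It is unlikely that placebo will increase oxygenation appreciably".

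The sample size paragraph in section 12 plans 19 patients per arm for 82% power to detect a gap of 0.40, with an achieved significance level of 0.0361.

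**The concern.** This is the only definition of the primary outcome, and taken in isolation it is ambiguous. If change means absolute change, a patient whose ratio falls from 300 to 240 has changed by 20% and is a success. Two harms would follow. Deteriorations among controls would raise the control success rate and dilute a real benefit. Deteriorations on nitric oxide would be credited to the drug.

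The two-sided test does not settle the matter, because it concerns the sign of the difference between arms and not the direction of each patient's change. Falls are also conceivable in this population. Section 5 describes respiratory failure as common after brain injury, and section 6 notes that oxygenation can fall when nitric oxide is withdrawn suddenly, though it calls this uncommon. With 38 evaluable patients, a few reclassified outcomes could alter the result.

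**Working it through.** **1. Reproduce the plan's figure.** Inputs from section 12: 19 per arm, success 0.50 against 0.10, two-sided pooled z-test at 0.05. Enumerate all 20 × 20 pairs of success counts (x, y) and reject when |z| ≥ 1.96, where z = (x/19 − y/19) / √[p(1 − p)(2/19)] and p = (x + y)/38. Summing the binomial probabilities of the rejected pairs gives:

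- power at 0.50 against 0.10: 0.815 (stated 82%)
- type I error at 0.10 against 0.10: 0.0361 (as stated)

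Defining success as an increase of 20% or more leaves these inputs, and so these results, as they are.

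**2. Apply the rule to a fall.** The usual percent change from baseline is (later − baseline)/baseline. For 300 to 240 it is (240 − 300)/300 = −0.20, which does not satisfy ≥ 0.20. A fall qualifies only if the analyst takes the absolute value, which the plan does not ask for.

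**3. What an either-direction rule would cost.** The documents give neither the spread of changes nor a deterioration rate, so every input in this step beyond 0.10, 0.50 and 19 per arm is an assumption.

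*(a) Control changes centred on zero, 10% of controls rising by 20% or more, treated patients shifted so that 50% do.*

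- Normal on the log scale: SD = ln 1.2/1.2816 = 0.1423. Control = 0.10 + Φ(ln 0.8/0.1423) = 0.158. Treated = 0.50 + Φ((ln 0.8 − ln 1.2)/0.1423) = 0.502. Power 0.656.
- Normal on the percent scale: SD = 0.20/1.2816 = 0.156. Control = 0.10 + 0.10 = 0.20. Treated = 0.50 + Φ(−0.40/0.156) = 0.505. Power 0.540.

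*(b) Rises held at 0.50 against 0.10, with assumed fall rates added to each arm.*

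| Falls, nitric oxide | Falls, placebo | Success rates | Exact power |
|---|---|---|---|
| 5% | 5% | 0.55 v 0.15 | 0.784 |
| 10% | 10% | 0.60 v 0.20 | 0.757 |
| 20% | 20% | 0.70 v 0.30 | 0.716 |
| 30% | 30% | 0.80 v 0.40 | 0.757 |
| 0% | 10% | 0.50 v 0.20 | 0.527 |
| 0% | 20% | 0.50 v 0.30 | 0.260 |
| 10% | 30% | 0.60 v 0.40 | 0.238 |

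*(c) The planning rates read as either-direction rates.* Take control changes centred on zero with SD 0.20/1.645 = 12.2 percentage points. Then 5% rise and 5% fall by 20% or more, which makes 10% in controls. A 20-point shift gives 0.50 + Φ(−0.40/0.122) = 0.5005 in treated patients. That is again 0.10 against 0.50, with power about 82%. So the 10% control rate does not by itself show which definition the planners had in mind.

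**4. Is a 20% fall by Day 3 documented?** The longitudinal evidence in section 5 (Background) concerns elastance and airways resistance, which worsened after day 5. The only PaO2:FiO2 figure given there is above 400 on day 1. Nothing cited shows the ratio falling by 20% by Day 3.

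**The case for a change.** The best case for acting is that evident intent makes the repair easy without making it unnecessary. A primary outcome should be codable from its own sentence, and a direction settled after the data are seen can be challenged as chosen to suit. The error could also be serious. With 10% improving in both arms, and 40% deteriorating on nitric oxide but none on placebo, an either-direction rule gives 0.50 against 0.10 and would favour nitric oxide with probability 0.815. Patients extubated during the 72-hour protocol are removed, so those analysed may include fewer of the best improvers.

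What stands is that the word increase is absent and that writing it would be tidier. The rest does not carry the point. Someone would have to choose to label deterioration a success in a trial whose hypothesis is better oxygenation, and that would be at least as open to challenge as coding an increase. Blood gases are recorded, so the sign of each change can be recovered and checked. Nor is there a neutral way to recast the criterion around the value just before gas delivery: that would replace the baseline-to-Day-3 window, which is a different question from direction.

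**Conclusion.** The concern does not call for a change. The endpoint sentence omits the direction, but the hypothesis, the label success, the planned rise from 0.10 to 0.50 and the placebo remark all point to an increase, and a signed 20% fall does not meet the threshold. No section says that a fall is a success. On the intended reading the effect is nil: 38 evaluable patients, 82% power (0.815 exact) and alpha 0.0361 all stand.

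The losses in the either-direction calculations, from none to a power of 0.238, depend wholly on assumed spreads and fall rates and show only how sensitive a misreading would be. The conclusion rests on one assumption, that the analyst codes the rule in line with the stated hypothesis. Saying increase in the analysis code or report, and describing large falls by arm, is ordinary good practice within the present plan.
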